D.5.1. Follow-up component – predicting pain in daily life: As a component of Specific Aim 3 and to translate the laboratory findings to participants’ daily environment, all participants will be contacted by phone once per week for four weeks following completion of study session 2. Participants will be asked to report on symptoms of pain (average and worst intensity), mood, sleep, disability, and interference of pain with daily activities over the preceding week using appropriate PROMIS items banks.¹¹¹ We have successfully used a similar approach in a previous project to collect weekly follow up data.⁹² Given that racial group differences in follow up data could be attributed to differences in treatments received or in comorbidities since completion of the experimental sessions, we will collect this information and control for these factors statistically, if needed.

D.6. Statistical methods

D.6.1. Statistical power: The power analysis for this study was completed with primary focus on the three hypotheses that comprise Specific Aim 1. We assumed the following race by SES interaction effect sizes for clinical pain severity (Cohen’s $f = .24$), perceived disability (Cohen’s $f = .19$), and functional performance difficulty (Cohen’s $f = .21$) derived from our pilot data. Effect size conventions are .10 (small), .25 (medium), and .40 (large). Probability value was set at .05 and the desired power was set at .85. According to these parameters and effect sizes, a total sample size of 240 participants is required to detect all of the race by SES interaction effects hypothesized for Specific Aim 1 (**Table 5**). These 240 participants will be allocated to four groups, such that there will be 60 low SES Blacks, 60 high SES Blacks, 60 low SES Whites, and 60 high SES Whites. Group sizes of 60 will provide greater than 95% power for detecting pair-wise differences while probing interaction effects based upon alpha level set as two-tailed $.05/6$ contrasts = .008 and Cohen’s d ranging from 0.83 to 1.90 (see C.2.1. above). We plan to over-enroll by 10% to accommodate for participant attrition. Therefore, 268 participants will be recruited with the expectation that at least 240 will complete.

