D.6.2. Data analysis: Data analysis will begin with calculating and comparing measures of central tendency (sample mean, sample median) and dispersion (sample variance, interquartile range) for all cLBP outcomes (e.g., PROMIS pain intensity, GCPS, ODI) as well as other study variables (CPM and TS, oxytocin, vitamin D, CRP levels, sleep, Perceived Injustice, Experiences of Discrimination, CES-D, etc.) according to race by SES groups. Confounding variables may include age, sex, pain medication use, engagement in treatments during the 4 week follow up period, and others as appropriate and will be considered as statistical controls.

Specific Aim 1: General Linear Models incorporating a 2x2 factorial design for Analysis of Covariance (ANCOVA) will be used to examine race by SES differences in cLBP outcomes including pain severity, disability, and functional performance. Race will include Blacks and Whites, while the Hollingshead Index will comprise the primary SES measure with participants split into high versus low SES according to previously published work.^{134,135} Significant interaction effects will be probed using pair-wise contrasts with Bonferroni-adjusted alpha levels to examine differences across racial and SES groups, with emphasis on low SES Blacks compared to high SES Whites. Additional

Table 5: Sample sizes needed to detect hypothesized race by SES differences in cLBP severity, perceived disability, and functional performance with $p < .05$ and power = .85.

Effect size (f)	Sample size needed
Clinical pain severity	.24
Perceived disability	.19
Functional performance	.21

analyses will be completed considering other indicators of high and low SES including subjective social status (MacArthur) and neighborhood SES. This will be done to determine which aspects of SES are most relevant to consider when addressing cLBP outcomes.

Specific Aim 2: The hypotheses that comprise this aim suggest that pain-relevant biopsychosocial factors including endogenous pain modulation, biomarkers, sleep, and psychosocial functioning will also differ according to racial and SES groups. These hypotheses will be tested using 2x2 ANCOVAs in the same manner indicated in Specific Aim 1. Significant race by SES interactions will be probed using pair-wise contrasts adjusted for multiple comparisons.

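### Aim 1 probes interactions with single-step Bonferroni over six contrasts; Holm's step-down would keep the same 5% bound, lose no rejection, and gain power for some moderate differences

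*Combined protocol and SAP*

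**What the plan says.** Section D.6.2, Specific Aim 1, tests race by SES in 2x2 ANCOVAs and then states: "Significant interaction effects will be probed using pair-wise contrasts with Bonferroni-adjusted alpha levels to examine differences across racial and SES groups". The contrasts therefore follow only a significant interaction. One comparison is singled out: "with emphasis on low SES Blacks compared to high SES Whites".

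Section D.6.1 gives the level: "alpha level set as two-tailed $.05/6$ contrasts = .008". It describes four equal cells ("60 low SES Blacks, 60 high SES Blacks, 60 low SES Whites, and 60 high SES Whites") and claims: "Group sizes of 60 will provide greater than 95% power for detecting pair-wise differences while probing interaction effects", for "Cohen’s d ranging from 0.83 to 1.90".

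For Specific Aim 2, D.6.2 says only: "Significant race by SES interactions will be probed using pair-wise contrasts adjusted for multiple comparisons". No method is named there. The plan mentions no step-down procedure and gives no reason for choosing Bonferroni in Aim 1.

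**The concern.** Single-step Bonferroni tests every one of the six contrasts at .05/6 = .0083, whatever the other five show. Holm's procedure orders the six p-values and compares them with .05/6, .05/5, .05/4, .05/3, .05/2 and .05, stopping at the first failure. It controls familywise error at .05 under any dependence, and it cannot miss a contrast that Bonferroni declares significant.

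The contrasts are what show which race and SES groups differ. Very large differences will be found either way. What is at stake is the moderate ones, such as a middle cell (low SES Whites or high SES Blacks) against high SES Whites. Those comparisons bear on whether low SES alone, or race alone, goes with worse outcomes.

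**Working it through.** **Inputs from D.6.1 and D.6.2:** 60 per cell, four cells, six contrasts, two-tailed .05/6, d from 0.83 to 1.90, interaction f = .24 (pain severity), .19 (disability) and .21 (functional performance), interaction alpha .05. **Assumed:** the patterns of cell means, a common SD and no covariate effect. The pilot values are in section C.2.1, which is not in the documents.

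**1. The plan's own figure.** The noncentrality is d·√(n/2) = 0.83 × √30 = 4.546, and the critical value at .05/6 is 2.638. Normal-approximation power is Φ(4.546 − 2.638) = 97.2%. The t distribution on 118 df gives 96.7%, or 96.6% with alpha rounded to .008. At d = 1.90 power is about 100%. The claim of more than 95% reproduces.

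**2. Ceiling on the gain at d = 0.83.** Holm's most lenient step is alpha .05, which gives Φ(4.546 − 1.960) = 99.5%. The gain cannot exceed 99.5 − 97.2 = 2.3 points.

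**3. Not every contrast can lie in the stated range.** Four ordered means have three adjacent gaps. If every difference were at least 0.83, the extremes would be 3 × 0.83 = 2.49 SD apart, more than 1.90. So for any one outcome at least one contrast is 1.90/3 = 0.63 or smaller.

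**4. Patterns that match the planned interaction.** In a balanced 2x2 with unit SD, f = |μ(low SES Black) − μ(high SES Black) − μ(low SES White) + μ(high SES White)| / 4. Put low SES Blacks at 1.90, high SES Whites at 0 and both middle cells at m, so f = (1.90 − 2m)/4:

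- m = .47: (1.90 − 0.94)/4 = .24
- m = .53: (1.90 − 1.06)/4 = .21
- m = .57: (1.90 − 1.14)/4 = .19

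All six pooled-SD contrasts (236 df) were simulated, keeping the runs with a significant interaction. Power for each middle cell versus the lowest cell:

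| f | d | Interaction significant | Bonferroni | Holm |
|---|---|---|---|---|
| .24 | .47 | 96% | 45% | 58% |
| .21 | .53 | 90% | 55% | 69% |
| .19 | .57 | 83% | 62% | 75% |

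The reason is simple. The three contrasts with low SES Blacks are almost always rejected, so Holm tests the next at .05/3 = .0167 and the one after at .05/2 = .025.

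**5. Patterns with little to gain.** One cell 0.83 SD from three equal cells gives f = 0.83/4 = .2075, also in line with the plan. Per-contrast power goes from 97.0% to 97.8% without conditioning on the interaction. Given a significant interaction, the gain is still under 1 point. With the same f values and an extreme contrast of 1.20 or 0.83, the remaining differences are about .22 or less and Holm adds 5 points or fewer.

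**6. Error.** Holm kept every Bonferroni rejection in every simulated data set. Attained familywise error was 4.2% for both under the global null. It was 2.2% (Bonferroni) and 4.2% (Holm) with one cell at 0.83, and 0.9% and 4.8% with means 1.9/.83/.83/0.

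**The case against.** Bonferroni is prespecified and valid, the contrasts were powered at exactly that level, and neither N = 240 nor the interaction tests depend on it. All of that stands, so this is a refinement and not a correction.

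Three further points also stand:

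- The attained error rates differ. Holm shares the 5% bound, but its extra power comes from error that Bonferroni leaves unspent.
- Bonferroni buys something: one fixed threshold and simultaneous intervals that agree with the decisions. A reader might infer that the plan gives power away for nothing, but that goes too far.
- The emphasised contrast, if it has the smallest p-value, is tested at .05/6 under Holm too and gains nothing.

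A reader might also take four equally spaced means spanning 1.90 SD and find power at d = .63 rising from 79% to 93%. The plan does not support that as a headline. With low SES Blacks and high SES Whites at the extremes, the interaction is 1.90 − 1.27 − 0.63 + 0 = 0, so the contrasts would be reached only about 5% of the time.

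Nor do the documents show a Bonferroni loss in Aim 2, whose contrast sentence names no method and already allows Holm. Step 3 does not refute the power claim either: the claim is limited to d from 0.83 to 1.90, and which contrasts that covers is set out in C.2.1.

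**Conclusion.** The point holds as a cheap improvement of low impact. That Holm is never less powerful and stays within the 5% familywise bound is a mathematical result and needs no assumption about the means. The size of the gain does need one. It is about 13 to 14 points for contrasts of d = .47 to .57 if the extreme cells are 1.90 SD apart and the middle cells equal. It is under 1 point if one cell stands 0.83 SD from three equal cells, and nil at d = 1.90. The actual gain cannot be established from the documents. The power statement in D.6.1 is correct and stays.

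**What to change.** In D.6.2, Specific Aim 1, replace the Bonferroni adjustment with Holm step-down adjusted p-values over the six pair-wise contrasts of each outcome. In Specific Aim 2, name the same Holm adjustment. Keep .05/6 in D.6.1 as a conservative planning value.

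The cost is one sentence in each aim, with no new data or participants. Bonferroni simultaneous intervals can be reported beside the Holm p-values, with a note that an interval may include zero for a contrast that is significant under Holm. If group data have already been examined, report the change as post hoc.

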D.1.1. Participants: We will recruit a total of 268 adult participants with cLBP with the expectation of approximately 10% attrition based upon the preliminary work of Drs. [name] and [name]. This will result in a final sample size of 240 (120 non-Hispanic Black, 120 non-Hispanic White) study completers. Participants between 19 and 85 years of age will be enrolled. Enrollment will begin almost immediately after funding is awarded because most of the study policies and procedures have already been established as part of the pilot work previously completed by the PI. The inclusion criteria for participants with cLBP are: 1) non-specific cLBP that has persisted for at least 3 months and has resulted in pain on at least half the days in the past 6 months; 2) age 19 – 85; the lower end of this age range was chosen in order to capture the growing prevalence of young adults with cLBP, and participants over 85 years are increasingly likely to meet one or more exclusion criteria; and 3) participants report ethnic group as non-Hispanic and racial group as either Black/African American or White/Caucasian. Participants with cLBP will be excluded if they have any concurrent medical conditions that could confound interpretation of outcome measures or coexisting disease that could preclude successful completion of the protocol (specific exclusion criteria are presented in the Protection of Human Subjects section).

Given that participants will be primarily recruited from a pain treatment clinic, it is reasonable to assume that many may be using daily opioid medications. We will not exclude participants using opioids daily as this could seriously hinder recruitment efforts or otherwise bias our sampling (e.g., only participants with low severity cLBP not receiving opioids). We are aware that both continued use and temporary withdrawal from these medications (should we ask participants to withhold) could affect pain perception. Therefore, participants will not be asked to withhold pain medications on the day of quantitative sensory testing. Rather, all medications currently being used for pain (e.g., opioids, NSAIDs, SSRIs, etc.) will be recorded and controlled in statistical analyses as needed.

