D.1.3. Demographic and SES measures: Ethnic and racial group will be determined by participant self-report using the standard Health and Human Services categories. We will recruit adults who report their ethnicity as non-Hispanic and their race as either Black/African American or White/Caucasian. Because racial groups often differ in socioeconomic status (SES),¹⁰³ and lower SES has been associated with increased risk of clinical pain¹⁰⁴ and increased prevalence of cLBP,¹⁰⁵ we will obtain a multidimensional battery of SES measures as part of this study. We will collect objective and subjective assessments of SES and social standing for individuals as well as the neighborhoods in which they live. The participant's self-reported educational attainment, annual household income, and occupational category will be used as an objective indicator of SES per the **Census Bureau Index of SES**.¹⁰⁶ The **Hollingshead Four-Factor Index of SES** will be used to assess four domains including educational attainment, retired/employed status, marital status, and occupational category/prestige.¹⁰⁷ The **MacArthur Scale of Subjective Social Status** will be used to measure participants' perceived social standing.¹⁰⁸ Research incorporating this measure has shown perceived social status to be determined by occupational position, education, household income, satisfaction with standard of living, and feelings of financial security regarding the future.^{108,109} We will match U.S. Census tract data to participants' addresses **to define neighborhood SES**.⁶⁸ Lastly, participants will self-report whether they currently have health insurance as well as quantity and quality of ongoing cLBP management.

D.2. Experimental session 1

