Specific Aim 3: The analytic strategy is designed to test the hypothesis that the biopsychosocial factors included in this study will differentially predict cLBP outcomes in Blacks compared to Whites, and furthermore that the strength of prediction will vary according to high versus low SES. We will use a multiple regression framework to build separate models for Blacks and Whites. Within these models, SES will be included as an effect moderator when examining the associations of biopsychosocial predictors (independent variables) with cLBP outcomes (dependent variables). To illustrate how models will be built and data used, we offer examples. Separate models will be built for Blacks and Whites to determine whether endogenous pain modulatory processes (e.g., CPM and TS) predict functional performance (e.g., SPPB and TUG). Within each model the SES variables will be added to examine interaction effects (i.e., moderation), such that the strength of prediction between endogenous pain modulation and functional performance will be greatest for those with low SES. The same process will be used to examine whether aggregated actigraphic sleep and diary data differentially predicts pain in everyday life (e.g., average ratings of pain intensity collected across 4 weeks of follow up) according to race and SES.

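### Neighborhood SES is a census-tract value, but the models named for it assume independent participants; if participants share tracts and outcomes correlate within them, its standard errors will be too small.

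*Combined protocol and SAP*

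**What the plan says.** Section D.1.3 of the combined protocol and SAP defines neighborhood SES by linkage to home addresses: "We will match U.S. Census tract data". The factor is therefore fixed within a tract and varies only between tracts.

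Section D.6.2 sets the Specific Aim 1 model: "General Linear Models incorporating a 2x2 factorial design for Analysis of Covariance (ANCOVA) will be used to examine race by SES differences". It also fixes the main measure of SES: "the Hollingshead Index will comprise the primary SES measure". That measure belongs to the individual. Neighborhood SES comes in afterwards, among the additional indicators: "analyses will be completed considering other indicators of high and low SES including subjective social status (MacArthur) and neighborhood SES". The stated purpose is to learn which aspects of SES matter most for chronic low back pain outcomes.

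Specific Aim 2 reuses the same 2x2 ANCOVAs. Specific Aim 3 uses multiple regression, separately by race: "Within each model the SES variables will be added to examine interaction effects". No section mentions a tract random effect, generalized estimating equations or cluster-robust standard errors. The neighborhood SES model is not written out, so independence of participants is implied by the models named and not stated outright.

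**The concern.** An ordinary general linear model computes its standard errors as if the residuals of all participants were independent. People in one tract share the neighborhood SES value and may also share local influences on pain that the model does not contain. If so, their residuals correlate positively, and the naive standard error of a factor that is constant within tracts is too small.

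What is at stake is the comparison among SES measures. Hollingshead and MacArthur vary from person to person; neighborhood SES is the only one of the three that is fixed within tracts. If its standard errors alone were materially understated, it could look more relevant than the others partly because of the error model.

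**Working it through.** **Inputs from the documents.** 240 completers, 60 in each of four race by SES cells; two-sided alpha .05; desired power .85; smallest interaction effect size f = .19 (section D.6.1). Tract-level definition of neighborhood SES (D.1.3). Models as named in D.6.2.

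**Inputs not in the documents (assumed).** Participants per tract, m, from 1 to 8; within-tract ICC of the residual outcome, up to .10.

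**The plan's own figure.** The 240 concerns the race by SES interaction. With a noncentral F, 1 numerator df, four cells and noncentrality f²N, f = .19 exactly needs 251, and power at 240 is .834. An unrounded f of about .1945 gives exactly 240, so rounding of f explains the gap. The other two effect sizes, .21 and .24, need 206 and 158. The documents give no figure for the neighborhood SES analysis.

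**Design effect.** For a factor constant within tracts of equal size m:

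- DE = 1 + (m − 1) × ICC
- true SE / naive SE = √DE
- effective N = 240 / DE
- actual type I error ≈ 2 × [1 − Φ(1.96 / √DE)]

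| m | ICC | DE | SE ratio | Effective N | Tracts (240/m) | Type I error |
|---|---|---|---|---|---|---|
| 1 | any | 1.000 | 1.000 | 240 | 240 | .050 |
| 1.5 | .05 | 1.025 | 1.012 | 234 | 160 | .053 |
| 2 | .05 | 1.050 | 1.025 | 229 | 120 | .056 |
| 4 | .05 | 1.150 | 1.072 | 209 | 60 | .068 |
| 4 | .10 | 1.300 | 1.140 | 185 | 60 | .086 |
| 8 | .10 | 1.700 | 1.304 | 141 | 30 | .133 |

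Example, m = 4 and ICC .10: DE = 1 + 3 × .10 = 1.30; √1.30 = 1.140; 240 / 1.30 = 185.

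**Check by simulation.** 240 people were scattered at random over tracts, so tract sizes were uneven. The outcome had a tract random intercept, SES was a binary tract-level factor, and a 2x2 ordinary least squares model was fitted (20,000 runs per setting). In mixed tracts race was 50:50; in segregated tracts it was 90:10 one way or the other. The entries are true SE over naive SE.

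| Tracts available | ICC | Neighborhood SES main effect | Interaction, mixed | Interaction, segregated |
|---|---|---|---|---|
| 200 | .02 | 1.02 | not run | 1.01 |
| 200 | .05 | 1.04 | not run | 1.02 |
| 120 | .05 | 1.05 | 1.00 | 1.03 |
| 60 | .05 | 1.10 | 1.00 | 1.06 |
| 40 | .10 | 1.25 | 1.00 | 1.17 |

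With 200 tracts there are on average 1.72 participants per occupied tract, and the excess reaches about 4% at ICC .05, slightly more than the equal-size formula gives. The interaction is protected in mixed tracts because the tract effect largely cancels when the two races are compared within a tract.

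**Does the remedy work?** In simulations with equal tracts of 2, 4 or 8 participants and ICC .05 or .10 (3,000 data sets per setting), tract-clustered standard errors brought nearly all error rates back to 5–6%.

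**The case against.** The strongest reply is that nothing shows the condition is met. A shared covariate value does not by itself bias standard errors; participants must share tracts and their residuals must correlate. The documents say only that "participants will be primarily recruited from a pain treatment clinic". They give no catchment area, and the stratification in section D.1.2 uses household income against the poverty line, not tract. At one to two participants per tract the effect is negligible or small. This stands, and it is why the point is conditional.

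It also stands that the hypotheses and power of Specific Aim 1 concern the interaction, which is hardly affected in racially mixed tracts, and that neighborhood SES is an additional analysis.

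Three stronger readings are tempting, and the documents do not support them:

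- *The standard errors are known to be too small.* Without tract counts or an ICC this cannot be said.
- *The effective sample is close to the number of tracts.* In the settings checked it stays nearer 240: 229, 185 and 141, against 120, 60 and 30 tracts.
- *The SES measures will be ranked by p-value, and only neighborhood SES is exposed.* The plan does not say how relevance will be judged. Race and individual SES may also cluster geographically and so be touched to some degree.

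What does not answer the point is the plan's silence. The models it names make no provision for tract, whatever the degree of sharing turns out to be.

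**Conclusion.** The point holds in conditional form and is a minor improvement, not a flaw in the main analysis. The direction is clear if participants share tracts and outcomes correlate positively within them. The size cannot be fixed from the documents: the true standard error for neighborhood SES exceeds the naive one by about 0–2.5% at one to two participants per tract with ICC up to .05 (up to about 4% with uneven tract sizes), about 14% at four per tract with ICC .10, and about 30% at eight per tract with ICC .10. The last case means 240 people in only 30 tracts. The matter becomes material only with heavy concentration in few tracts or a high ICC.

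The race by neighborhood SES interaction is affected appreciably only when tracts are both shared and racially segregated. A reader should not carry the point over to the primary Hollingshead analysis or to the sample of 240; neither rests on the tract-level factor.

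**What to change.** Add to section D.6.2 that, for every analysis using neighborhood SES, the report will give the number of tracts and the distribution of participants per tract. State that these models will use standard errors clustered on census tract with a small-sample correction. A tract random intercept is an alternative where enough tracts hold several participants; if most tracts hold one person, its variance can barely be estimated. The Hollingshead and MacArthur models can stay as planned.

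The cost is a few sentences and an analysis option, since address-to-tract matching is already planned. Intervals for neighborhood SES become slightly wider. If few tracts are shared, results will hardly change, and the tract counts will show why.

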D.1.2. Initial screening: All participants will undergo a cLBP screening interview using the recently developed research standards for defining cLBP proposed by the Research Task Force of the NIH Pain Consortium.⁹⁰ This will involve a review of each participant's UAB electronic medical record to confirm cLBP status and assess the reported duration of cLBP, current and past treatments for cLBP, comorbid conditions, and current medication use. Using the joint clinical practice guidelines from the American College of Physicians and the American Pain Society,⁵⁸ patients with cLBP will be placed into 1 of 3 broad categories: 1) nonspecific cLBP, 2) cLBP potentially associated with radiculopathy or spinal stenosis, or 3) cLBP potentially associated with another specific spinal cause. Patients placed into category 3 will be excluded if the cause of cLBP is determined to be ankylosing spondylitis, cancer or other malignancy, or in the context of autoimmune disease or other widespread pain condition (e.g., lupus, fibromyalgia). The screening will also assess demographic, SES, and health history information to ensure that no other exclusion criteria are

[figure not shown]

Figure 7: Flow diagram depicting matriculation through the study protocol.

present. To ensure that a relatively equal number of Blacks and Whites with high and low SES are recruited, a stratified sampling approach will be incorporated for recruitment. This will be done by determining whether a participant falls above or below the poverty line (as a proxy for overall SES) based upon reported annual household income and number of occupants residing within the family/household using the 2015 HHS poverty guidelines.¹⁰¹ In 2015 Alabama was the 6th poorest state in the Union, with 13% of Whites and 31% of Blacks living below the poverty line.¹⁰² Therefore, we are confident in our ability to recruit individuals with high and low SES.

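### Aim 3 states a hypothesis about how prediction differs between races, but specifies only separate race-specific regressions and no test that compares them

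*Combined protocol and SAP*

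**What the plan says.** Under Specific Aim 3 in section D.6.2, the plan says its strategy is designed to test whether "the biopsychosocial factors included in this study will differentially predict cLBP outcomes in Blacks compared to Whites", and also whether the strength of prediction varies with SES.

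The method follows: "We will use a multiple regression framework to build separate models for Blacks and Whites". SES enters each of these models as an effect moderator. The worked example (pain modulation predicting functional performance) repeats the structure, with SES interactions added inside each race's model. Sleep and follow-up pain are handled alike: "The same process will be used to examine whether aggregated actigraphic sleep and diary data differentially predicts pain in everyday life".

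Three other statements bear on the point:
- Covariates (D.6.2): "Confounding variables may include age, sex, pain medication use, engagement in treatments during the 4 week follow up period", and others as appropriate.
- SES coding, given under Aim 1: "the Hollingshead Index will comprise the primary SES measure with participants split into high versus low SES". Aim 3 refers only to SES variables and does not say how they are coded.
- Sample size (D.6.1): "The power analysis for this study was completed with primary focus on the three hypotheses that comprise Specific Aim 1".

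**The concern.** The hypothesis has two parts. The SES part is tested by the SES-by-predictor terms within each race. The race part concerns whether a predictor's association with an outcome differs between two groups, and two regressions fitted side by side do not answer that. They supply two slopes and two standard errors; a test needs the difference between the slopes and its uncertainty.

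Without a stated rule, nothing prevents a result that is significant in one race and not in the other from being reported as differential prediction. That pattern is not evidence that the slopes differ. Racial disparity is the study's subject, so a spurious claim of this kind would matter.

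**Working it through.** **1. Is there a between-race comparison anywhere in the plan?**

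| Part of plan | What is compared | Race comparison of slopes? |
|---|---|---|
| Aim 1, 2x2 ANCOVA | Outcome means by race and SES | No |
| Aim 2, 2x2 ANCOVA | Means of the biopsychosocial factors by race and SES | No |
| Aim 3, separate regressions | Predictor slopes by SES, within each race | No |
| D.6.1, power | Aim 1 interactions and pair-wise mean contrasts | No |

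No race-by-predictor term, pooled model, slope difference or test of equal coefficients appears. I read differential prediction as a difference in slopes. If a difference in correlation or R-squared was meant, the gap is the same, since no between-race comparison of any kind is stated.

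**2. The plan's own figure.** No figure is given for Aim 3. The stated total of 240 belongs to Aim 1. By noncentral F (1 df, four cells), f = .19 at 240 gives power .834 against the target of .85, and f of about .1945 gives .85. That gap is within rounding of the printed f and has no bearing here.

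**3. What one informal reading rule would do.** Inputs: 120 completers per race (D.1.1); two-sided .05 (the level set in D.6.1, assumed for Aim 3); the same true correlation r in both races (assumed). With p the power in one race (noncentral t), the chance that exactly one race is significant is 2p(1 - p):

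| r | p | 2p(1 - p) |
|---|---|---|
| 0 | .050 | .095 |
| .10 | .194 | .313 |
| .20 | .602 | .479 |
| .30 | .927 | .135 |
| .40 | .997 | .005 |

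Simulated within-race models with an SES-by-predictor term and 60 per cell gave 9%, 30%, 48%, 17% and 0.6% with effect-coded SES, and 10%, 20%, 45%, 44% and 18% with dummy-coded SES. Coding matters because under dummy coding the predictor coefficient is the slope in one SES stratum only. A direct test of the slope difference rejected 4.4% to 5.6% under either coding.

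**4. Power of a direct test.** Fisher z, 120 per race: SE = sqrt(2/117) = .1307. Power = Phi(q/SE - z), with q = atanh(r) for 0 versus r.

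| 0 versus r | q/SE | Power, z = 1.960 (.05) | Power, z = 3.113 (.05/27) |
|---|---|---|---|
| .20 | 1.551 | 34% | 6% |
| .30 | 2.367 | 66% | 23% |
| .40 | 3.240 | 90% | 55% |

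The simulated slope test gave 34%, 64% and 88% with 60 per cell. Recruitment is stratified on the poverty line (D.1.2), while Aim 1 splits on Hollingshead, so cells of 60 are not assured. With assumed 90/30 and 30/90 cells, power is 26%, 50% and 77%. For standardized variables the 95% interval is about 1.96 x sqrt(2/120) = +/-0.25.

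**5. Multiplicity.** The 27 is an assumed count: nine variables named in D.6.2 times three outcome domains. The expected number of false differences is 27 x .05 = 1.35, but only if all 27 true differences are zero.

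**6. Are pooled and separate fits interchangeable?** Simulation, equal slopes of .20, 60 per cell, predictor variance 1 versus .25 (all assumed). With residual SD 1 versus 2, ordinary pooled least squares rejected about 9% to 10%; with the SDs reversed, about 1.5%. The separate-model test stayed near 5% in both. If only the residual SD differs (1 versus 1.5), pooled least squares holds at about 5%.

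Covariates raise a similar issue. With a covariate effect of .4 in one race and 0 in the other, and predictor-covariate correlations of .2 to .5 (assumed), a pooled model with a common covariate term rejected 9.5% to 33.1%. With race-by-covariate terms it rejected 4.8% to 4.9%.

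**The case against.** Fitting by race is legitimate, the models are presented partly as examples, the study was sized mainly on Aim 1, and both slopes with their standard errors will exist. An analyst could subtract them later without new data. All of that is true, and it limits severity. It does not supply the missing test: separate models are set as the general method before the examples begin, and for Aims 1 and 2 the plan does spell out interaction tests and adjusted contrasts.

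A reader might infer that fitting by race is itself an error, or that Aim 3 as a whole is invalid. The documents do not support this. The separate models validly address SES moderation within each race and can be kept.

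A reader might also infer that the plan carries a false-positive rate of up to 48%. It does not. No passage says a race difference will be read from significance in one race only, and the correlations are assumed. The count of 27 is equally soft: the list of variables in D.6.2 is open-ended, pain summation is measured by two modalities at two sites, and follow-up pain is a further outcome.

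**Conclusion.** The concern holds as a structural gap: the race half of the Aim 3 hypothesis, including sleep as a predictor of four-week follow-up pain, has no pre-specified between-race test. This conclusion rests on the text and needs no assumed effect size. It should be fixed, but it does not touch Aims 1 and 2 or the within-race SES tests.

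The illustrative rates in step 3 show why a rule is needed; they are not properties of this plan. The power figures are single-predictor approximations without covariates. They suggest that only fairly large race differences would be detected: 80% power is reached at about 0 versus .35.

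**What to change.** Add to Aim 3:

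- **Test.** Keep the separate models. For each predictor-outcome pair, test slope(Black) minus slope(White), with standard error sqrt(se1^2 + se2^2) and a 95% confidence interval. Use common units: unstandardized, or scaled by the full-sample SD.
- **Alternative.** Fit one pooled model with all lower-order terms, race x predictor, race x SES x predictor, and race x covariate for every covariate used. Use heteroscedasticity-robust or race-specific residual variances; ordinary pooled least squares is not equivalent when predictor and residual variances both differ by race.
- **SES.** If SES is high/low, code it +1/2, -1/2. If it is continuous, center it at the same full-sample value in both races. The compared slopes then refer to the same SES mix. Apply this to each SES measure used.
- **Claims.** Claim a race difference only from this test, never from significance in one race only. Test the three-way term if a race-by-SES difference in prediction is claimed.
- **Multiplicity and scope.** Label the Aim 3 race comparisons exploratory, or adjust across a listed set of pairs. State that the study was sized on Aim 1 and that a non-significant difference does not show equal slopes.

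The cost is SAP wording and no new data. The drawback is low power, as shown in step 4. The three-way term is weaker still: with 60 per cell and 85% power, it detects a difference of differences of about 0.79 on the Fisher-z scale.
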